## GOALS

We are researching a novel neuromodulatory platform using visual stimulation for its impact on nociception. We hypothesize that short abstract videos can be optimized to be used in the modulation of nociception utilizing the process called Dynamic Visual Neuromodulation (DVN). DVN optimization will be performed through an iterative process of choosing different arrangements of concurrent stimulation parameters in order to enhance neurophysiological response. Since pain experiments are challenging, DVN optimization has been designed to be carried out in two stages in order to decrease the burden on participants: (1) In Experiment 1 we aim to develop an optimization procedure for inducing arousal; this experiment requires no pain induction. (2) Using the same general procedure, the Experiment 2 will pursue further optimization of the visual stimuli with the aim of inducing arousal to decrease nociception and the perception of experimentally induced pain in healthy subjects.

## OBJECTIVES

The objective of the current research is to develop a visual stimulation platform capable of modulating nociception and alleviating perceived pain intensity. Dandelion Science (the Sponsor) hypothesizes that controlling the level of arousal through DVN can reduce nociceptive effects caused by experimentally produced painful stimuli in healthy participants.

[figure not shown]
- Aim 1: Find dynamic visual stimuli capable of reliably modulating physiologic arousal.

- Aim 2: Validate EEG, GSR, ECG, and EMG, biomarkers of pain.

- Aim 3: Demonstrate that optimized DVN can modulate nociception and mitigate or modify pain perception in healthy participants\*.

## BACKGROUND

In 2017, 11 million of the 191 million prescriptions written for opioid pain medications were misused; 35% of opioid-related deaths (nearly 17,000 cases) were connected to these prescriptions (*7 Staggering Statistics About America's Opioid Epidemic*, 2016). Researchers have been looking - with limited success (Nascimento et al., 2019) - for reliably safe and effective opioid-sparing therapies. The challenge is the complexity of pain (Murphy et al., 2017). Pain comes in many forms, is highly subjective (Fillingim, 2017; Krupić et al., 2019; Pisanu et al., 2019), and arises from complex neural data-processing across multiple regions of the brain (Fenton et al., 2015; Wiech, 2016). This complexity makes it challenging to deliver pain relief that is both safe and effective. Opioids offer efficacy but not safety. While clinical pain-relief interventions (e.g. cognitive behavioral therapy, CBT) and digital behavioral methods (e.g. guided meditation, distraction, and electronic CBT) are safe, none so far has been fully successful (Nascimento et al., 2019).

The technology platform most compatible with this approach is neuromodulation, which makes use of direct, reproducible input - typically electrical or magnetic stimuli (Kumar & Rizvi, 2014) - and interacts with the CNS as a system of complex data-processing neural networks (Herculano-Houzel, 2009).

Preliminary study data show that visual stimuli with certain dynamic features are able to induce neurologic and physiologic state changes.

## INCLUSION AND EXCLUSION CRITERIA FOR THE EXPERIMENTS

Participants will be recruited at the Dandelion Science's lab [REDACTED]. The details pertaining to the recruitment procedures will be submitted in site-specific applications to the IRB. On the day of the experiment the participants will be encouraged to have a good night sleep and instructed to abstain from consuming caffeinated beverages and medical drugs.

### ***INCLUSION CRITERIA***

- Participants of both sexes
- Participants of diverse ethnic and racial backgrounds
- Subjects who speak, read, and understand English and are willing and able to provide written informed consent on an IRB-approved form prior to the initiation of any study procedures
- Age range: 18-50

The age limitation reflects differences in pain response thresholds both in terms of mean and variance, across different developmental groups (González-Roldán et al., 2020; Tumi et al., 2017). Moreover, the age range stated above is the target group of individuals of greatest interest for this future intervention (Salmond & Allread, 2019).

### ***EXCLUSION CRITERIA***

A medical history questionnaire will be provided to determine which participants will need to be excluded.

The following criteria will be used to exclude people from the study:

- Patients with neurologic, endocrine, renal, gastrointestinal, and chronic pain disease
- Participants who use unprescribed drugs or medications (a urine drug test will be administered on the day of the experiment to verify compliance)
- Chronically medicated participants
- Participants with photosensitivity and patients with epileptic seizures
- Participants who have undergone major surgery within two months of the experiment date
- Patients with cardiac disorders
- Women who are pregnant
- Prisoners
- People who are unable to provide consent
- Individuals diagnosed with a psychiatric disorder that is likely to interfere with the conduct of the study
- Participants with implanted electronic devices of any kind, including pace-makers, electronic infusion pumps, stimulators, defibrillators or similar

## STUDY-WIDE NUMBER OF PARTICIPANTS

Up to 120 participants

## STUDY-WIDE RECRUITMENT METHODS

Participants for the study will be recruited by the Dandelion's personnel using social networks and personal communications.

## STUDY TIMELINES

	Stages	Au g	Se p	O ct	No v	De c	Ja n	Fe b	Ma r	Apr	Ma y	Jun	Jul
	Recruitment												
Arousal optimization	Experiment												
	Analysis												
	Recruitment												
Pain optimization	Experiment												
	Analysis												

## STUDY ENDPOINTS\*

Successful control of the arousal reduction of pain perception as measured by VAS and ERP for either thermal (CHEPs) or electric shock pain induction. While there is no single criterion for determining a clinically significant threshold, Dandelion Science has adopted the reported criterion of 20% reduction in pain intensity and expects to achieve a pain perception reduction of 20% on VAS scale for AI-guided visual stimulation as compared with no-visual-stimulation in response to at least one of the nociceptive conditions (CHEPs stimulation).

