### ***Conditions***

Up to three pain intensities levels (cold: 3°C, innocuous: 35°C, hot: 52°C) with OVS.

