#### ***EEG data preprocessing:***

Cleaning EEG data involves removing artifacts from the EEG signal. Although the EEG system is designed to record neural activity, it also records electrical activity arising from physiological entities such as eye blinking or jaw clenching. The EEG will be digitized continuously at a 512 Hz sampling rate. Data will be downsampled to 256 Hz and bandpass filtered using a 0.1 Hz high-pass cut-off (12db/octave) to reduce low-frequency noise such as drifting, and a 30 Hz low-pass cut-off (24db/octave) to reduce high-frequency noise such as muscle tension. Following this step, data will then be re-referenced to the average of all channels. Then a time-frequency analysis will be performed to extract temporal dynamics of the major EEG wave bands (alpha, beta, theta and gamma). Signal processing will be performed using the MNE toolbox (Gramfort et al., 2013) and performed in Python. In addition, the painful stimulation-onset ERPs will be computed and the areas of N2 and P2 components will be used for the analysis.

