#### ***Optimization training and testing\*:***

During the optimization procedure, we will use alpha and beta EEG bands, number of peaks in GSR, heart-rate variability and facial EMG spectrum, among other features, to guide the arousal and pain-control optimization procedure. The success of the optimized stimuli in reducing pain

perception will be evaluated using VAS. Prior data indicate that the minimal clinically relevant change in pain self-report should be 20%. In our study this effect will correspond to roughly an 8 mm change on the 100mm VAS. If the true difference in the mean response of matched pairs is 8 mm, we will need a sample of 30 participants to be able to reject the null hypothesis that the response difference is zero with a probability (power) of 0.8. The Type 1 error probability of this test is 0.05.

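### Success is allowed in any one nociceptive condition, but the 0.05 type 1 error is stated for one VAS test with no condition named and no adjustment

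*Combined protocol and SAP*

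**What the plan says.** The combined protocol and SAP treats the pain endpoint in several places.

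- **Study Endpoints** describes the outcome "as measured by VAS and ERP for either thermal (CHEPs) or electric shock pain induction". Its only numeric criterion is a 20% reduction on the VAS, optimized stimulation against no visual stimulation, "in response to at least one of the nociceptive conditions (CHEPs stimulation"). The reduction is worded as something the sponsor expects to achieve.
- **Experiment 2, Conditions** lists "Up to three pain intensities levels (cold: 3°C, innocuous: 35°C, hot: 52°C) with OVS". No condition without visual stimulation is listed.
- **Experiment 2, Equipment and instruments** lists CHEPs as the only source of nociception.
- **EEG data preprocessing** says that "the areas of N2 and P2 components will be used for the analysis", with no threshold, test or alpha attached.
- **Optimization training and testing** says that the VAS will be used to judge whether the stimuli reduce pain. It equates the 20% with "roughly an 8 mm change on the 100mm VAS" and asks for 30 participants to "reject the null hypothesis that the response difference is zero with a probability (power) of 0.8". It adds: "The Type 1 error probability of this test is 0.05".

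Nowhere does the plan name a primary condition, a test order or a multiplicity adjustment.

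**The concern.** A rule that is satisfied by any one of several conditions gives more than one chance of success. The stated error rate belongs to one comparison. If the conditions are tested separately at that rate and the best one is reported, the chance of a false claim is higher than the plan says. This endpoint carries Aim 3, that optimized stimulation can modulate nociception and pain perception. With no condition named in advance, the choice could be made after the results are seen, and in few participants: Experiment 2 plans 20 against the 30 calculated.

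**Working it through.** **Inputs from the documents.** Difference 8 mm, power 0.80, type 1 error 0.05, n = 30 (Optimization training and testing); planned size 20 (Experiment 2); up to three thermal levels, one innocuous, so at most two that could be noxious (Conditions).

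**Assumptions.** The documents do not give the SD of the paired differences, whether the test is one- or two-sided, or the correlation between conditions. I take the test as two-sided, because the null is a zero difference, and vary the correlation from 0 to 0.8.

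**1. The plan's own figure.** The figure of 30 cannot be reproduced forward, because "If the true difference in the mean response of matched pairs is 8 mm" is not accompanied by an SD. It can be solved backward:

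- Normal approximation: SD = 8 × √30 / (1.960 + 0.842) = 43.82 / 2.802 = 15.6 mm.
- Paired t-test (noncentral t), two-sided: SD = 15.1 mm. This value is used below.

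With an SD of 15.1 mm, one test at 0.05 has power 0.80 at n = 30 and 0.61 at n = 20.

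**2. Error of an either-level rule on VAS.** Each level is tested at two-sided 0.05 and either can count. If independent, the family-wise error is 1 − 0.95² = 0.0975. In the pain-reducing direction alone it is 1 − 0.975² = 0.0494. The correlated values are bivariate normal probabilities with cut-off 1.96.

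| Correlation | Any significant result, two-sided | False pain reduction only |
|---|---|---|
| One pre-named test | 5.0% | 2.5% |
| 0 | 9.8% | 4.9% |
| 0.5 | 9.1% | 4.5% |
| 0.8 | 7.8% | 3.9% |

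The false-claim rate is therefore multiplied by about 3.9 / 2.5 = 1.6 to 4.9 / 2.5 = 2.0.

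**3. Power if the rule is kept and adjusted.** With two levels, the first Holm step uses 0.05 / 2 = 0.025. At an SD of 15.1 mm:

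- Power for a given level at 0.025 is 0.70 at n = 30 and 0.49 at n = 20.
- Power for at least one win at n = 30, if 8 mm holds in both levels, is 1 − (1 − 0.70)² = 0.91 if independent. By simulation it is about 0.85 at correlation 0.5 and 0.79 at 0.8.

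**The case against.** Several points can be made for the plan.

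- **There may be only one test.** The parenthesis after the any-condition wording names CHEPs, which is the only pain device in Experiment 2. If the intended choice was between modalities, and CHEPs in one condition is the answer, 0.05 stands. This reading is possible, but the plan does not state it. CHEPs delivers more than one level, and the text does not say which one is tested or whether the levels are pooled. The cold level is also uncertain: it is 3°C under Conditions and 40 °C in the CHEPs procedure. Those passages must be reconciled.
- **The endpoint states an expected effect, not a test per condition.** This stands, and it is why the error rates above are conditional. If success meant only an observed mean reduction of at least 8 mm, the false-success chance per level with an SD of 15.1 mm would be 1 − Φ(8√30/15.1) = 1 − Φ(2.90) = 0.002 at n = 30, and 1 − Φ(2.37) = 0.009 at n = 20. For either of two independent levels it would be about 0.004 and 0.018. The plan does not adopt that rule either. The only decision rule it describes is the 0.05 test that it links to 8 mm.
- **A wrong-direction result cannot meet the endpoint.** This is correct. The directional error for two levels stays just under 5%. The comparison that matters is with the 2.5% of a single two-sided test.
- **This is early work in healthy volunteers.** That argues for a light remedy, and one is available.

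A reader might also infer that ERP adds further chances, by counting VAS, N2 and P2 in each level as four or six separate tests. The documents do not support this. VAS and ERP are joined by *and*, the numeric criterion is on the VAS alone, and success in reducing pain is judged by the VAS. If both measures were required, the error for either of two independent levels would fall to about 0.5% to 4.3% (correlation 0 to 0.8 between the measures).

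**Conclusion.** The concern holds in a limited form. The endpoint is worded as an any-condition rule, while the 0.05 is given for one matched-pairs VAS test with no condition named. If the two non-innocuous levels are each tested on VAS at two-sided 0.05 and either counts, the family-wise error is about 7.8% to 9.8%, and a false pain-reduction claim has a chance of about 3.9% to 4.9% instead of 2.5%. This rests on two assumptions: that each level is tested separately, and that both are noxious conditions that can meet the endpoint.

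It would go too far to say that the stated 0.05 is wrong. It is correct for the test it describes; the gap is that it is not tied to the success rule. The role of ERP is unclear and should be stated, but it is not shown to be an extra route to success. Electric shock is named in the endpoint but has no procedure or equipment entry, so it is not counted as a further chance.

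**What to change.** In Study Endpoints and in Optimization training and testing:

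1. Name one primary test: the mean paired VAS difference, optimized versus no visual stimulation, in one pre-named CHEPs condition (for example the hot level), at two-sided 0.05.
2. Label the other level and the N2 and P2 areas as secondary or supportive.
3. Delete the any-condition wording and the mention of electric shock, which has no procedure.

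This keeps alpha at 0.05 and the calculated size at 30. The price is that a finding in the non-primary level becomes secondary.

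If the any-condition rule is kept, apply Holm across the noxious CHEPs levels at an overall 0.05 and restate the power. State both the power for a given level (0.70 at n = 30, 0.49 at n = 20) and the power for at least one win (about 0.79 to 0.91 at n = 30 if 8 mm holds in both), with the SD they rest on.

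Either way, more than the endpoint wording has to change. The no-visual-stimulation comparator must be written into the Experiment 2 conditions, which list levels only with optimized stimulation. The cold temperatures under Conditions and in the CHEPs procedure must also be reconciled.

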## PROCEDURES INVOLVED

The study consists of 2 experiments:

## Experiment 1. Optimization of visual stimulation for arousal

In this experiment we will use the participant's response to dynamic visual stimulation to modify and adapt the stimuli to drive a stronger arousal response. The goal is to show that visual stimulation can affect participants by both raising and lowering their arousal level.

Location	Dandelions Science Research Facilities 
Estimated number of participants	Up to 100
Estimated experiment duration	2 hr 10 min

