### Conditions

1. Optimized visual stimulation (**OVS**)
2. Random visual stimulation control (**RVS**)

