## ***Approximate trial and block structure***

1. Fixation cross - 1 second.
2. Stimulation - 5 to 15 seconds total.
3. Behavioral response - 5 to 15 seconds.

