### *Effectiveness of DVN in controlling arousal*

Dandelion Science will also collect the responses to randomly chosen parameters. This data will be used to estimate the quality of the signal and variance in responses and serve as a prior distribution for the Bayesian model.

After we collect data for the baseline, we will compare the average response curve (a biomarker value for multiple participants over the course of random stimulation) with the response curve during the optimization procedure. We expect that after a few iterations, the biomarker values will diverge from the baseline. The required number of iterations to observe the effect is yet to be defined.

We want to test whether optimization leads to the gradual improvement in the ability of stimulation to cause change in arousal as registered by the biomarkers. To do so we will analyze how the biomarker changed with control stimulation (RVS) versus optimized stimulation (OVS). The divergence of the time series will be calculated using the ARIMA model, and the significance of the diversion will be assessed using the Chow Test.

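### Experiment 1 sets out to show that video raises and lowers arousal, but its only control is random video, so the planned contrast cannot give the direction of change from an unstimulated level

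*Combined protocol and SAP*

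**What the plan says.** The opening of Experiment 1 in the combined protocol and SAP sets a goal in two directions: "The goal is to show that visual stimulation can affect participants by both raising and lowering their arousal level".

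The Conditions section lists two conditions, OVS and RVS. The second is described as "Random visual stimulation control". Both are videos. No blank-screen, neutral or rest condition is listed.

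Under Effectiveness of DVN in controlling arousal, the baseline curve is "a biomarker value for multiple participants over the course of random stimulation". The test is then described: "To do so we will analyze how the biomarker changed with control stimulation (RVS) versus optimized stimulation (OVS"). Divergence is to be modelled with ARIMA and its significance assessed with a Chow test; no direction is stated. The Pilot section confirms that the control baseline comes from 5 to 10 participants shown clips with randomly chosen parameters.

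The Optimization method section mentions a shift of a biomarker from its own baseline value. This is one of several aims for choosing the next parameters; the value is not defined and does not reappear in the effectiveness test.

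Each trial opens with "Fixation cross - 1 second", followed by the clip (5 to 15 s) and a response stage (5 to 15 s). The analysis does not name the fixation as a reference.

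A no-video comparator appears in Study Endpoints, for pain on the VAS: "as compared with no-visual-stimulation".

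**The concern.** Raising and lowering are statements about change from some reference level. Read plainly, the goal is about what video does to a person, so the natural reference is the same person without video. The plan supplies another video instead.

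Random clips may not be inert. The Background reports that stimuli with certain dynamic features change neurologic and physiologic state, and randomly drawn parameters may include such features. If random clips raise arousal, a clip that leaves it unchanged, or raises it less, falls below RVS and appears to lower it. If random clips lower arousal, the raising half of the goal fails in the same way.

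At stake is the stated conclusion of Experiment 1: carried out as written, the plan could report a direction of effect that it has not measured. It would also not show how far OVS moves arousal from the no-video reference against which pain reduction is later judged.

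**Working it through.** The documents give no effect size, SD, alpha or power for arousal, so there is no planned figure to reproduce. The only power statement, under Optimization training and testing, concerns pain on the VAS.

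**1. What the contrast identifies.** Set the mean biomarker level without video to 0, under RVS to r and under OVS to v, with higher values meaning more arousal.

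- Planned contrast: v − r.
- Quantity in the goal: v − 0 = v.
- Discrepancy: (v − r) − v = −r.

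The plan never measures r. If r = 0 the two quantities agree. If r > 0, any v with 0 ≤ v < r gives a negative contrast although OVS does not lower arousal. If r < 0, any v with r < v ≤ 0 gives a positive contrast although OVS does not raise it.

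**2. How much this could matter (illustration, two-group).** Assumptions, none from the documents: one summary value per person, between-person SD 1, two-sided alpha 0.05, v = 0, and RVS participants drawn only from the pilot. The documents supply the ceiling of 100 participants in Experiment 1 and the pilot size of 5 to 10. Counting the pilot within that ceiling gives splits of 90/10 and 95/5.

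Noncentrality = r × √(n₁n₀/(n₁+n₀)), with df = 98 and critical t = 1.984.

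- 90/10: √(90×10/100) = 3.00
- 95/5: √(95×5/100) = 2.18

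Chance of a significant OVS-below-RVS result when OVS truly does nothing:

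| r (SD) | 90 OVS / 10 RVS | 95 OVS / 5 RVS |
|---|---|---|
| 0 | 2.5% | 2.5% |
| 0.1 | 5% | 4% |
| 0.3 | 14% | 9% |
| 0.5 | 32% | 19% |
| 0.8 | 66% | 41% |
| 1.0 | 84% | 58% |

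The split matters: at r = 0.5, 50/50 gives noncentrality 0.5 × 5 = 2.5 and 70%. A negative r makes false lowering rarer than 2.5% and moves the problem to the raising direction.

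**3. The same question with a paired comparison (illustration).** Measure in SDs of the paired difference and use the normal approximation Φ(|v − r|√n − 1.96).

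- r = 1.0, v = 0.5 (OVS truly raises arousal): |v − r| = 0.5, so OVS is significantly below RVS 61% of the time at n = 20, 94% at n = 50 and 99.9% at n = 100.
- r = 0.5, v = 0.2 (OVS truly raises arousal): |v − r| = 0.3, giving 27%, 56% and 85%.

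A larger sample therefore makes the misreading more likely, because the discrepancy is a bias and not noise.

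**4. Whether another part of the plan supplies the reference.** The 1 s fixation is not named in the analysis and is short for GSR peak counts or heart-rate variability, two of the features that guide optimization. The response stage may be video-free, but it follows the clip and is taken up by rating. The 45 s breaks and the sensor calibration of about 5 minutes are not assigned to any analysis either.

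**The case against.** The strongest reply is that RVS is the right control for the question the effectiveness section poses: whether optimization progressively improves the ability of stimulation to change arousal. It holds constant the act of watching a moving display, which a blank screen does not. That stands, and RVS should stay for that question.

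The plan also mentions a shift from a biomarker's own baseline value. This shows that such a reference was in mind, but it steers parameter selection, is undefined, and is not used in the effectiveness test.

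A reader might infer more than the documents support:

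- *That Aim 1 fails altogether.* It does not. If OVS and RVS truly differ, at least one of them differs from no video, so video has modulated arousal. Only the direction is unidentified.
- *That the fixation is the only video-free time in a trial.* The trial structure has a separate 5 to 15 s response stage.
- *That Experiment 2 inherits a wrong sign.* Its Bayesian model is pretrained on Experiment 1 data, not on the OVS-RVS contrast. Its hypothesis concerns arousal-inducing stimuli, so a lowering label has no stated use there.
- *That the sign is wrong whenever the OVS-RVS gap is smaller than r.* For positive r this applies only to downward gaps; OVS above RVS above zero has the correct sign.
- *That the percentages are error rates of this trial.* They come from a t-test or its paired analogue with assumed splits. The plan uses ARIMA and a Chow test, which as described has no direction, and the Background does not say which way random clips would push arousal.

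**Conclusion.** The concern holds for the direction of effect. The planned contrast can show that optimized clips differ from random clips. It cannot support the statement that visual stimulation raises, or lowers, arousal from an unstimulated level.

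The discrepancy equals the effect of random video against no video. It vanishes if that effect is zero; the plan neither measures it nor argues that it is zero. With assumed effects of 0.1 to 1.0 SD, the two-group illustration puts false lowering between 4% and 84%, against a nominal 2.5%. This shows how sensitive the conclusion is to an unmeasured quantity and does not estimate the trial's error rate. The logical point needs none of those assumptions: it follows from the stated goal, the two listed conditions and the definition of the baseline curve.

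**What to change.** Under Conditions and Approximate trial and block structure for Experiment 1, add a no-video trial: a fixation-only screen of clip length, followed by the same SAM rating, once per block at a random position. Under Effectiveness of DVN in controlling arousal, judge raising and lowering by the signed within-participant difference OVS minus no-video. Keep OVS minus RVS for whether optimization beats random choice.

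Cost: a trial lasts 1 + 5 + 5 = 11 s to 1 + 15 + 15 = 31 s. In a block of about 180 s that is 11/180 = 6% to 31/180 = 17% of the optimization trials. Over 25 blocks it gives 25 no-video trials per participant, with no added participants or equipment. The trials interrupt the adaptive sequence, and response to the preceding clip may carry over into them; random placement spreads this carry-over but does not remove it.

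If the trial type is not added, restate the Experiment 1 goal and conclusion as raising or lowering arousal relative to random clips. That costs only wording.

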## ***Data Analysis***

### *Optimization method*

In the optimization procedure, Dandelion Science defines the visual stimulation (VS) parameters and, while they are presented, monitor the response to them. Once the response is registered, we select the next set of parameters that is expected to achieve one or more of the following goals:

- identify and explore in detail VS parameters that affect a specific biomarker (i.e. that cause a significant shift in the biomarker in comparison with its baseline value);
- find the specific values for VS parameters that drive a combination of biomarkers to a predefined state (“target state”);
- improve our general predictive model of the relationship between VS parameters and bioresponse.

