## **Experiment 2. Optimization of visual stimulation for pain perception**

In this experiment we will optimize visual stimulation with the goal of reducing pain perception. To reduce the burden on participants, optimization has been designed as a two-step process, with the first step (implemented in Experiment 1) requiring no pain induction. Our preliminary hypothesis is that arousal-inducing visual stimuli will reduce the perception of acute pain, based on the well-known phenomenon of stress-induced analgesia (Vachon-Presseau et al., 2013; Yilmaz et al., 2010). Thus, once we optimize the stimuli to affect arousal state in Experiment 1, we will test the effectiveness of the optimized visual stimuli (OVS) in reducing pain perception and carry out additional adjustments to further increase their impact.

Location	Dandelions Science Laboratory 
Estimated number of participants	20 participants
Estimated experiment duration	2 hr

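### Experiment 1 aims to show that arousal can be both raised and lowered, but its single OVS condition and non-directional Chow test cannot support a two-way claim

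*Combined protocol and SAP*

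**What the plan says.** - **Goal.** The introduction to Experiment 1 wants stimulation shown to work in two directions, "by both raising and lowering their arousal level". The sentence before it describes adaptation one way only, to "modify and adapt the stimuli to drive a stronger arousal response".
- **Conditions (Experiment 1).** Two are listed: "Optimized visual stimulation" and "Random visual stimulation control". OVS is not divided into raising and lowering.
- **Optimization method (Experiment 1).** One of several possible aims is to "find the specific values for VS parameters that drive a combination of biomarkers to a predefined state". Whether that state is high or low arousal is not given, nor is any rule for assigning a target to a participant, session or block.
- **Effectiveness of DVN in controlling arousal.** An average curve over participants under random stimulation is compared with the curve during optimization. The two are expected to diverge. Divergence is calculated with an ARIMA model, and "the significance of the diversion will be assessed using the Chow Test". No sign, no contrast per direction and no success criterion per direction is stated.
- **Experiment 2, introduction.** The working hypothesis needs one direction: "arousal-inducing visual stimuli will reduce the perception of acute pain".

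**The concern.** The goal makes two claims, that arousal can be pushed up and that it can be pushed down. The analysis answers one question: do OVS and RVS differ? A positive answer fits three situations: OVS only raises arousal, OVS only lowers it, or it does both in different runs. Only the third meets the goal, and the planned test does not separate it from the other two.

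The plan could therefore report success on its divergence test without evidence for the claim it set out to make. If runs with opposite targets were combined, genuine two-way control could also look weak or absent. Direction matters downstream too, because Experiment 2 is motivated by raised arousal in particular.

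**Working it through.** **No figure to reproduce.** Experiment 1 has up to 100 participants, with no power, alpha or effect size for the arousal comparison. The one power statement (Optimization training and testing: 30 participants, 8 mm) concerns the VAS pain outcome and is not used here.

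**1. Does the test carry a sign?** With k coefficients per series and n observations in each of the two series, the Chow statistic is

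F = [(RSS_pooled − RSS_OVS − RSS_RVS) / k] / [(RSS_OVS + RSS_RVS) / (2n − 2k)].

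Reversing the sign of all the data reverses every residual and leaves every sum of squares, and so F, unchanged. A numerical check with an intercept and linear trend (k = 2, n = 25, hence 2 and 46 degrees of freedom) gave p = 1.63e-05 for a data set and the same p for its mirror image.

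**2. What could OVS contain?**
- One target direction only: the test can detect it, but the other half of the goal has no data.
- Both directions, analysed separately: the goal could be met, but no such analysis is written.
- Both directions, pooled: opposite shifts are averaged.

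The documents do not say which applies.

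**3. Size of the dilution, if opposite targets are pooled.** Let a share p of the pooled OVS series shift by +d and the rest by −d:

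mean shift = p·d + (1 − p)·(−d) = (2p − 1)d.

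At p = 0.6 this is 0.2d.

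The table adds rejection rates from an illustrative simulation of the Chow test on averaged curves. Its assumptions are 20 participants per curve, 25 iterations (matching the 25 experimental blocks, though the plan does not equate blocks with iterations), SD 1 within iteration, linear drift reaching ±d SD at the last iteration, independent errors, no ARIMA step, alpha 0.05 and 3,000 replicates. Apart from the 25, these values are not from the documents.

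| Share aimed up, p | Mean shift | Rejection, d = 0.25 | Rejection, d = 0.5 |
|---|---|---|---|
| 1 | d | 0.51 | 0.99 |
| 0.75 | 0.5d | 0.15 | 0.50 |
| 0.5 | 0 | 0.05 | 0.05 |
| 0.25 | −0.5d | 0.15 | 0.50 |
| 0 | −d | 0.51 | 0.98 |

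The table is symmetric apart from simulation error, so the test cannot tell all-up from all-down. An even mix rejects only at the alpha level.

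**4. Price of separating the directions, same illustration.** With 10 OVS participants per direction, each set compared with an RVS curve also averaged over 10, the Chow test rejects in about 0.82 of replicates at d = 0.5 and 0.27 at d = 0.25. If the two comparisons are independent, both succeed with probability about 0.82 × 0.82 = 0.67 or 0.27 × 0.27 = 0.07.

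**The case against.** The strongest reply is that this is missing detail rather than a faulty design.

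- **Pooling is not stated.** The Effectiveness section attaches averaging to the random-stimulation curve. It does not say that OVS curves are averaged over participants, still less over opposite targets. This stands. A reader might infer that opposite effects will cancel, or that one direction is bound to go untested. The documents support neither as a fact, and the figures in the table apply only if pooling occurs.
- **The target state is set beforehand, so its direction is known.** This stands in part. The wording permits separate high and low targets, but nothing says that both will be set, how they will be assigned, or that they will be analysed apart.
- **Direction can be read from the fitted curves or from the SAM arousal ratings.** True as description. Neither is written into the planned inference, and neither could separate runs already combined.
- **The two-way goal is one sentence.** Aim 1 and the numbered goals of Experiment 1 speak neutrally of modulating or manipulating arousal. This is a good argument for narrowing the sentence as an alternative repair. It does not make the sentence and the test agree.
- **Experiment 2 inherits a model, not a p-value.** Its Bayesian model is pretrained on Experiment 1 data, and further adjustment is planned. This stands: the documents do not make stimulus selection depend on the Chow result, so the harm to Experiment 2 should not be overstated.

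A reader might also divide the 25 blocks of a session between OVS and RVS to cost a split. The documents do not support that either. The Pilot section collects a random-stimulation control in 5 to 10 separate participants, and nothing says that the two conditions share a session.

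**Conclusion.** The mismatch is real on the text. The goal has two directions, the optimized condition is undivided, and the sole inferential step is blind to sign. Followed as written, the analysis could establish that OVS and RVS differ, but not that arousal was both raised and lowered.

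That conclusion needs no assumption beyond the Chow test being an F test. The dilution is conditional on pooling opposite targets. Given pooling and equal opposite effects, it ranges from none at p = 1 or p = 0 to complete at p = 0.5; unequal mixes weaken the signal without removing it. The rejection rates are illustrative only.

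This should be settled before Experiment 1 is analysed, and preferably before OVS runs are scheduled. It does not invalidate the experiment as development work.

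**What to change.** **Conditions and Optimization method (Experiment 1).** Fix the target direction, raise or lower, of each OVS optimization run in advance, and record it. Keep each run sequential, for example by assigning direction per participant or per session. Interleaving raise, lower and random blocks within a participant would break up the series on which gradual improvement is judged and would invite carryover.

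**Effectiveness of DVN in controlling arousal.** State that opposite targets are never pooled. Name the arousal biomarker and the sign that means higher arousal. Test two signed contrasts, OVS-raise above RVS and OVS-lower below RVS, and claim two-way control only if both succeed. Because both are required, each can be tested at the full alpha with no split. If either alone were to count as success, multiplicity would need control.

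**Alternative.** If only raised arousal is pursued, narrow the goal sentence in the introduction to Experiment 1 to raising, and test that one signed contrast.

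**Cost.** The changes are to wording, target assignment and the analysis text. The two-direction option leaves fewer OVS runs per direction and so less power for each. The size of that loss cannot be computed, because the documents do not give the allocation of blocks or participants between OVS and RVS and leave the required number of iterations undefined. It should be worked out once the allocation is fixed, and the number of participants checked against it.
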